#### **10.1.2 Financial disclosure**

Insurance coverage will be handled according to local requirements.

Finance and insurance are addressed in the Investigator and/or CRO agreements, as applicable.

### **10.1.3 Informed consent process**

Study participant's informed consent must be obtained and documented in accordance with local regulations, ICH-GCP requirements, and the ethical principles that have their origin in the principles of the Declaration of Helsinki.

Prior to obtaining informed consent, information should be given in a language and at a level of complexity understandable to the study participant in both oral and written form by the Investigator (or designee). Each study participant will have the opportunity to discuss the study and its alternatives with the Investigator.

Prior to participation in the study, an IEC-approved, written ICF should be signed and personally dated by the study participant and by the person who conducted the informed consent discussion (Investigator or designee) prior to the initiation of any study-specific assessment at the Screening Visit. The study participant must receive a copy of the signed and dated ICF. As part of the consent process, each study participant must consent to direct access to his/her medical records for study-related monitoring, auditing, IEC review, and regulatory inspection.

If the ICF is amended during the study, the Investigator (or the Sponsor, if applicable) must follow all applicable regulatory requirements pertaining to the approval of the amended ICF by the IEC and use of the amended form.

The study participant may withdraw his/her consent to participate in the study at any time. A study participant is considered as enrolled in the study when he/she has signed the ICF. An eCRF must not be started, nor may any study specific procedure be performed for a given study participant, without having obtained his/her written consent to participate in the study.

### **10.1.4 Data protection**

UCB staff (or designee) will affirm and uphold the study participant's confidentiality. Throughout this study, all data forwarded to UCB (or designee) will be identified by the study participant's randomization number.

The Investigator agrees that representatives of UCB, its designee, representatives of the relevant IEC, or representatives of regulatory authorities will be allowed to review that portion of the study participant's primary medical records that directly concerns this study (including, but not limited to, laboratory test result reports, ECG reports, admission/discharge summaries for hospital admissions occurring during a participant's study participation, and autopsy reports for deaths occurring during the study).

The study participant must be informed that his/her personal study-related data will be used by the Sponsor in accordance with local data protection law. The level of disclosure must also be explained to the study participant.

The study participant must be informed that his/her medical records may be examined by Clinical Quality Assurance auditors or other authorized personnel appointed by the Sponsor, by appropriate IEC members, and by inspectors from regulatory authorities.

### **10.1.5 Committees structure**

Not applicable.

## **10.1.6 Data quality assurance**

The Sponsor will supervise study initiation visits to verify the qualifications of the Investigators, inspect the facilities, and inform the Investigators of responsibilities and procedures for ensuring adequate and correct documentation.

The Investigators must prepare and maintain adequate and accurate records of all observations and other data pertinent to the clinical study for each study participant. Frequent communication between the clinical unit and the Sponsor is essential to ensure that the safety of the study is monitored adequately. The Investigators will make all appropriate safety assessments on an ongoing basis.

All aspects of the study will be carefully monitored with respect to GCP and standard operating procedures (SOPs) for compliance with applicable government regulations. The Study Monitor will be an authorized individual designated by the Sponsor. The Study Monitor will have access to all records necessary to ensure the integrity of the data and will periodically review the progress of the study with the Investigators. Remote monitoring visits may be conducted during the COVID-19 pandemic or under other exceptional circumstances as deemed appropriate to ensure study participants' safety.

The Investigator must permit study-related monitoring, audits, IEC review, and regulatory agency inspections and provide direct access to source data documents.

The Sponsor or designee is responsible for the data management of this study including quality checking of the data.

Study Monitors will perform ongoing source data verification to confirm that data entered into ClinBase by authorized site personnel are accurate, complete, and verifiable from source documents; that the safety and rights of participants are being protected; and that the study is being conducted in accordance with the currently approved protocol and any other study agreements, ICH GCP, and all applicable regulatory requirements.

All essential documents are to be retained by the Investigator until at least 2 years after the last approval of a marketing application in an ICH region and until there are no pending or contemplated marketing applications in an ICH region, or at least 2 years have elapsed since the formal discontinuation of clinical development of the IMP/investigational device. These documents should be retained for a longer period, however, if required by the applicable regulatory requirement(s) or by an agreement with UCB (CPMP/ICH/135/95, 2002 [Section 4.9.5]). The Investigator will contact UCB for authorization prior to the destruction of any study records or in the event of accidental loss or destruction of any study records. The Investigator will also notify UCB should he/she relocate or move the study-related files to a location other than that specified in the Sponsor's TMF.

### **10.1.6.1 Case Report form completion**

The Investigator is responsible for prompt reporting of accurate, complete, and legible data in ClinBase and in all required reports.

Any change or correction to ClinBase after saving must be accompanied by a reason for the change.

Corrections made after the Investigator's review and approval (by means of a password/electronic signature) will be reapproved by the Investigator.

The Investigator should maintain a list of personnel authorized to enter data into ClinBase.

#### **10.1.6.2 Apps**

Not applicable.

#### **10.1.7 Data collection and source documents**

PAREXEL will use ClinBase to collect medical data during this study.

All source documents must be accurate, clear, unambiguous, permanent, and capable of being audited. They should be made using some permanent form of recording (ink, typing, printing, optical disc). They should not be obscured by correction fluid or have temporary attachments (such as removable self-stick notes).

Source documents are original records in which raw data are first recorded. These may include hospital/clinic/general practitioner records, charts, diaries, x-rays, laboratory results, printouts, pharmacy records, care records, ECG or other printouts, completed scales, quality of life questionnaires, or video, for example. Source documents should be kept in a secure, limited access area.

Source documents that are computer generated and stored electronically must be printed for review by the monitor (eg, ECG reports). Once printed, these copies should be signed and dated by the Investigator and become a permanent part of the study participant's source documents.

If source documents have been captured by ClinBase, they need to be electronically signed/stamped to indicate review by the Investigator/designee/delegate.

The Investigator/designee will facilitate the process for enabling the monitor to compare the content of the printout and the data stored in the computer to ensure all data are consistent.

#### **10.1.8 Study and site closure**

The Sponsor designee reserves the right to close the study site or terminate the study at any time for any reason at the sole discretion of the Sponsor. Study sites will be closed upon study completion. A study site is considered closed when all required documents and study supplies have been collected and a study-site closure visit has been performed.

The Investigator may initiate study-site closure at any time, provided there is reasonable cause and sufficient notice is given in advance of the intended termination.

Reasons for the early closure of a study site by the Sponsor or Investigator may include but are not limited to:

- Failure of the Investigator to comply with the protocol, the requirements of the IEC or local health authorities, the Sponsor's procedures, or GCP guidelines
- Inadequate recruitment of study participants by the Investigator
- Discontinuation of further IMP development

The study must be discontinued if the positive evaluation or approval is withdrawn by the IEC or local health authority.

### **10.1.9      Publication policy**

The results of this study may be published or presented at scientific meetings. If this is foreseen, the Investigator agrees to submit all manuscripts or abstracts to the Sponsor before submission. This allows the Sponsor to protect proprietary information and to provide comments.

The Sponsor will comply with the requirements for publication of study results. In accordance with standard editorial and ethical practice, the Sponsor will generally support publication of multicenter studies only in their entirety and not as individual site data. In this case, a coordinating Investigator will be designated by mutual agreement.

Authorship will be determined by mutual agreement and in line with International Committee of Medical Journal Editors authorship requirements.

This document cannot be used to support any marketing application and any extensions or variations thereof.  
PUBLIC COPY

## 10.2 Appendix 2: Clinical laboratory tests

The tests detailed in [Table 10-1](#) below will be performed at SYNLAB Analytics & Services (safety laboratory assessments) and Parexel International (urinalysis/urine drug screen).

Protocol-specific requirements for inclusion or exclusion of study participants are detailed in [Section 5.1](#) and [Section 5.2](#) of this protocol.

Additional tests may be performed at any time during the study as determined necessary by the Investigator or required by local regulations.

**Table 10-1: Protocol-required safety laboratory assessments**

Laboratory measurements	Variables
Serology/virology	HbsAg, HBc-Ab (both IgG and IgM), HCV-Ab, HIV1-Ab, HIV1-Ag, HIV-2 Ab, SARS-CoV-2 RT-PCR a
Hematology	Complete blood count, ie, hemoglobin, hematocrit, RBC, WBC, WBC with differential, platelet count
Coagulation/hemostasis	Prothrombin time, aPTT
Clinical chemistry	Albumin, ALP, ALT, AST, GGT, creatine kinase, LDH, total bilirubin, BUN, creatinine, glucose, total cholesterol, LDL cholesterol, HDL cholesterol, triglycerides, electrolytes (sodium, potassium, chloride, total calcium), and total protein, FSH
Urine (dipstick) b	pH, protein, glucose, ketone, urobilinogen, bilirubin, blood, specific gravity, nitrite, and leukocytes
Urine alcohol test/drug screen	Ethanol will be measured using a urine alcohol test. Urine drug screen includes amphetamines/methamphetamines, barbiturates, benzodiazepines, tetrahydrocannabinol, cocaine, tricyclic antidepressants, phencyclidine, and morphine/opiates
Pregnancy	Prior to dosing, a serum pregnancy test (hCG) will be performed; post dosing the test may be performed in urine. The FSH test will be performed in postmenopausal women at the Screening Visit.

ALP=alkaline phosphatase; ALT=alanine aminotransferase; aPTT=activated partial thromboplastin time; AST=aspartate aminotransferase; BUN=blood urea nitrogen; FSH=follicle stimulating hormone; GGT=gamma glutamyltransferase; HBc-Ab=hepatitis B core antibody; HBsAg=hepatitis B surface antigen; hCG=human chorionic gonadotropin; HCV-Ab=hepatitis C virus antibody; HDL=high density lipoprotein; HIV=human immunodeficiency virus; HIV1/2-Ab=HIV1/2 antibody; HIV1-Ag=HIV1 antigen; LDH=lactate dehydrogenase; IgG=immunoglobulin G; IgM=immunoglobulin M; LDL=low density lipoprotein; RBC=red blood cell; RT-PCR=real-time reverse transcriptase polymerase chain reaction; SARS-CoV-2=severe acute respiratory syndrome coronavirus 2; WBC=white blood cell

a Sample will be obtained via pharyngeal swab.

b Upon a positive urine test for leukocytes, blood, nitrite, or protein, the Investigator may require further urine analysis, such as flow cytometry. Results of additional urine analyses will be included in the database. If the flow cytometry examination shows a different result than the urine dipsticks, the urine will be investigated by fully

---

automated digital imaging where leukocytes, erythrocytes, and casts (cellular, granular, hyaline) in urine will be analyzed.

This document cannot be used to support any marketing authorization application and any extensions or variations thereof.

PUBLIC COPY

## **10.3 Appendix 3: Adverse events – definitions and procedures for recording, evaluating, follow up, and reporting**

### **10.3.1 Definition of AE**

AE Definition

• An AE is any untoward medical occurrence in a patient or clinical study participant, temporally associated with the use of IMP, whether or not considered related to the IMP.

• NOTE: An AE can therefore be any unfavorable and unintended sign (including an abnormal laboratory finding), symptom, or disease (new or exacerbated) temporally associated with the use of IMP.

Events Meeting the AE Definition

• Any abnormal laboratory test results (hematology, clinical chemistry, or urinalysis) or other safety assessments (eg, ECG, radiological scans, vital signs measurements), including those that worsen from baseline, considered clinically significant in the medical and scientific judgment of the Investigator (ie, not related to progression of underlying disease).

• Exacerbation of a chronic or intermittent pre-existing condition including either an increase in frequency and/or intensity of the condition.

• New conditions detected or diagnosed after IMP administration even though it may have been present before the start of the study.

• Signs, symptoms, or the clinical sequelae of a suspected drug-drug interaction.

• Signs, symptoms, or the clinical sequelae of a suspected overdose of either IMP or a concomitant medication. Overdose per se will not be reported as an AE/SAE unless it is an intentional overdose taken with possible suicidal/self-harming intent. Such overdoses should be reported regardless of sequelae.

Events NOT Meeting the AE Definition


• Any clinically significant abnormal laboratory findings or other abnormal safety assessments which are associated with the underlying disease, unless judged by the Investigator to be more severe than expected for the study participant's condition.

• The disease/disorder being studied or expected progression, signs, or symptoms of the disease/disorder being studied, unless more severe than expected for the study participant's condition.

• Medical or surgical procedure (eg, endoscopy, appendectomy): the condition that leads to the procedure is the AE.

• Situations in which an untoward medical occurrence did not occur (social and/or convenience admission to a hospital).

• Anticipated day-to-day fluctuations of pre-existing disease(s) or condition(s) present or detected at the start of the study that do not worsen.

### 10.3.2 Definition of SAE

If an event is not an AE per definition above, then it cannot be an SAE even if serious conditions are met (eg, hospitalization for signs/symptoms of the disease under study, death due to progression of disease).

A SAE is defined as any untoward medical occurrence that, at any dose:	
a. Results in death	
b. Is life-threatening	
The term 'life-threatening' in the definition of 'serious' refers to an event in which the study participant was at risk of death at the time of the event. It does not refer to an event, which hypothetically might have caused death, if it were more severe.

c. Requires inpatient hospitalization or prolongation of existing hospitalization	
In general, hospitalization signifies that the study participant has been detained (usually involving at least an overnight stay) at the hospital or emergency ward for observation and/or treatment that would not have been appropriate in the physician's office or outpatient setting. Complications that occur during hospitalization are AEs. If a complication prolongs hospitalization or fulfills any other serious criteria, the event is serious. When in doubt as to whether "hospitalization" occurred or was necessary, the AE should be considered serious.
 
Hospitalization for elective treatment of a pre-existing condition that did not worsen from baseline is not considered an AE.

d. Results in persistent disability/incapacity	

The term disability means a substantial disruption of a person's ability to conduct normal life functions.

This definition is not intended to include experiences of relatively minor medical significance such as uncomplicated headache, nausea, vomiting, diarrhea, influenza, and accidental trauma (eg, sprained ankle) which may interfere with or prevent everyday life functions but do not constitute a substantial disruption.

e. Is a congenital anomaly/birth defect	
f. Is an important medical events:	

Medical or scientific judgment should be exercised in deciding whether SAE reporting is appropriate in other situations such as important medical events that may not be immediately life-threatening or result in death or hospitalization but may jeopardize the study participant or may require medical or surgical intervention to prevent one of the other outcomes listed in the above definition. These events should usually be considered serious.

Examples of such events include, but are not limited to, potential Hy's law, invasive or malignant cancers, intensive treatment in an emergency room or at home for allergic bronchospasm, blood dyscrasias, or convulsions that do not result in hospitalization, or development of drug dependency or drug abuse.

### 10.3.3 Recording and follow up of AE and/or SAE

AE and SAE Recording

When an AE/SAE occurs, it is the responsibility of the Investigator to review all documentation (eg, hospital progress notes, laboratory reports, and diagnostics reports) related to the event.

The Investigator will then record all relevant AE/SAE information in the eCRF.

It is not acceptable for the Investigator to send photocopies of the study participant's medical records to UCB in lieu of completion of the UCB AE/SAE eCRF page.

There may be instances when copies of medical records for certain cases are requested by UCB. In this case, all study participant identifiers, with the exception of the study participant number, will be redacted on the copies of the medical records before submission to UCB.

The Investigator will attempt to establish a diagnosis of the event based on signs, symptoms, and/or other clinical information. Whenever possible, the diagnosis (not the individual signs/symptoms) will be documented as the AE/SAE.

Assessment of Intensity

The Investigator will make an assessment of intensity for each AE and SAE reported during the study and assign it to 1 of the following categories:
 

Mild: An event that is easily tolerated by the study participant, causing minimal discomfort and not interfering with everyday activities.

Moderate: An event that causes sufficient discomfort and interferes with normal everyday activities.

Severe: An event that prevents normal everyday activities. An AE that is assessed as severe should not be confused with a SAE. Severe is a category utilized for rating the intensity of an event; and both AEs and SAEs can be assessed as severe.

An event is defined as 'serious' when it meets at least 1 of the predefined outcomes as described in the definition of an SAE, NOT when it is rated as severe (eg, a severe AE may be either serious or not serious, depending on whether these criteria are also met).

 
The National Cancer Institute Common Terminology Criteria for Adverse Events (NCI-CTCAE) should be used as a supportive standardization instrument to evaluate AEs and SAEs but the final intensity grading by the Investigator must be mild, moderate, or severe.

### Assessment of Causality

- The Investigator is obligated to assess the relationship between IMP and each occurrence of each AE/SAE.
- A “reasonable possibility” of a relationship conveys that there are facts, evidence, and/or arguments to suggest a causal relationship, rather than a relationship cannot be ruled out.
- The Investigator will use clinical judgment to determine the relationship.
- Alternative causes, such as underlying disease(s), concomitant therapy, and other risk factors, as well as the temporal relationship of the event to IMP administration will be considered and investigated.
- The Investigator will also consult the IB and/or Product Information, for marketed products, in his/her assessment.
- For each AE/SAE, the Investigator **must** document in the medical notes that he/she has reviewed the AE/SAE and has provided an assessment of causality.
- There may be situations in which an SAE has occurred and the Investigator has minimal information to include in the initial report to UCB. However, **it is very important that the Investigator always make an assessment of causality for every event before the initial transmission of the SAE data to UCB.**
- The Investigator may change his/her opinion of causality in light of follow-up information and send a SAE follow-up report with the updated causality assessment.
- The causality assessment is one of the criteria used when determining regulatory reporting requirements.

### Follow-up of AEs and SAEs

- The Investigator is obligated to perform or arrange for the conduct of supplemental measurements and/or evaluations as medically indicated or as requested by UCB to elucidate the nature and/or causality of the AE or SAE as fully as possible. This may include additional laboratory tests or investigations, histopathological examinations, or consultation with other health care professionals.
- An AE should be followed until it has resolved, has a stable sequelae, the Investigator determines that it is no longer clinically significant, or the study participant is lost to follow up. This follow-up requirement applies to AEs, SAEs, and AEs of special interest.
- If a study participant dies during participation in the study or during a recognized follow-up period, the Investigator will provide UCB with a copy of any post-mortem findings including histopathology.
- New or updated information will be recorded in the originally completed eCRF.
- The Investigator will submit any updated SAE data to the UCB within 24 hours of receipt of the information.

## Reporting of SAEs

### SAE Reporting to UCB via an Electronic Data Collection Tool

- The primary mechanism for reporting an SAE to UCB will be the electronic data collection tool.
- If the electronic system is unavailable for more than 24 hours, then the site will use the paper SAE data collection tool (see next section).
- The site will enter the SAE data into the electronic system as soon as it becomes available.
- After the study is completed at a given site, the electronic data collection tool will be taken off-line to prevent the entry of new data or changes to existing data.
- If a site receives a report of a new SAE from a study participant or receives updated data on a previously reported SAE after the electronic data collection tool has been taken off-line, then the site can report this information on a paper SAE form (see next bullet) or to the UCB Study Physician by telephone.
- Contacts for SAE reporting can be found in [SERIOUS ADVERSE EVENT REPORTING](#).

This document cannot be used to support any marketing authorization application and any extensions or variations thereof.  
PUBLIC COPY

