#### **8.3.1 Time period and frequency for collecting AE and SAE information**

All AEs and SAEs will be collected from the signing of the ICF and at the time points specified in the schedule of activities (Section 1.3).

In order to ensure complete safety data collection, all AEs occurring during the study (ie, after the signing of the ICF), including any pretreatment and posttreatment periods required by the protocol, must be reported in the CRF even if no study medication was taken but specific study procedures were conducted. This includes all AEs not present prior to the initial visit and all AEs that recurred or worsened after the initial visit.

All SAEs will be recorded and reported to the Sponsor or designee within 24 hours, as indicated in Appendix 4 (Section 10.4). The Investigator will submit any updated SAE data to the Sponsor within 24 hours of it being available.

The Investigator is specifically requested to collect and report to UCB (or its representative) any SAEs (even if the Investigator is certain that they are in no way associated with the IMP), up to 30 days from the end of the study for each study participant, and to also inform study participants of the need to inform the Investigator of any SAE within this period. Serious AEs that the Investigator thinks may be associated with the IMP must be reported to UCB regardless of the time between the event and the end of the study.

The method of recording, evaluating, and assessing causality of AE and SAE and the procedures for completing and transmitting SAE reports are provided in Appendix 3 (Section 10.3).

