#### **8.3.6 Adverse events of special interest**

An AE of special interest is any AE that a regulatory authority has mandated be reported on an expedited basis, regardless of the seriousness, expectedness, or relatedness of the AE to the administration of a UCB product/compound.

For bimekizumab, the following event requires immediate reporting (within 24 hours, regardless of seriousness) to UCB:

- Hy's Law
  - Potential Hy's Law, defined as  $\geq 3 \times \text{ULN}$  ALT or AST with coexisting  $\geq 2 \times \text{ULN}$  total bilirubin in the absence of  $\geq 2 \times \text{ULN}$  ALP, with no alternative explanation for the biochemical abnormality (ie, without waiting for any additional etiologic investigations to have been concluded). Follow-up information should be reported if an alternative etiology is identified during investigation and monitoring of the study participant.

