## 10.7.6 Reporting of SAEs

### SAE reporting to UCB via an electronic data collection tool

- The primary mechanism for reporting an SAE to UCB will be the electronic data collection tool.
- If the electronic system is unavailable, then the site will use the paper SAE data collection tool (see next section) in order to report the event within 24 hours.
- The site will enter the SAE data into the electronic system as soon as it becomes available.
- After the study is completed at a given site, the electronic data collection tool will be taken off-line to prevent the entry of new data or changes to existing data.
- If a site receives a report of a new SAE from a study participant or receives updated data on a previously reported SAE after the electronic data collection tool has been taken off-line, then the site can report this information on a paper SAE form (see next section) or to the UCB Medical Monitor by telephone.
- Contacts for SAE reporting can be found in [SERIOUS ADVERSE EVENT REPORTING](#).

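### Section 10.3.3 calls for the paper SAE form only after more than 24 hours of system downtime, which conflicts with the 24-hour reporting duty in Section 8.3.1 and the fallback rule in Section 10.7.6

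*Protocol*

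**What the plan says.** Three places in the protocol bear on this.

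- **Section 8.3.1** sets the duty: "All SAEs will be recorded and reported to the Sponsor or designee within 24 hours". Updated information has the same limit: "The Investigator will submit any updated SAE data to the Sponsor within 24 hours of it being available". The section sends the reader to Appendix 3 (Section 10.3) for completing and transmitting SAE reports.
- **Section 10.3.3** (Appendix 3) makes the electronic tool the primary route and gives this fallback: "If the electronic system is unavailable for more than 24 hours, then the site will use the paper SAE data collection tool". It repeats the limit for updates: "The Investigator will submit any updated SAE data to the UCB within 24 hours of receipt of the information".
- **Section 10.7.6** (device appendix, also headed as reporting of SAEs) gives the same fallback with no waiting time. For an outage of whatever length, its instruction is: "then the site will use the paper SAE data collection tool (see next section) in order to report the event within 24 hours". The paper procedure that follows it covers facsimile, and telephone where there is no facsimile equipment.

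The note in Section 8.3.7 says that device events meeting the AE or SAE definition also go through Appendix 3, so such an event falls under both fallback rules.

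**The concern.** The fallback exists so that an SAE still reaches the sponsor on time when the electronic tool is down. A trigger that needs more than 24 hours of downtime is longer than the whole time allowed for reporting. It can therefore leave a site with no prescribed route until the deadline has passed.

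Section 10.3.3 is also the text that Section 8.3.1 directs the site to, so this is the rule a site would find first. The telephone option in Section 10.3.3 applies only once the tool has been taken off-line after study completion at the site, so it does not cover an outage during the study.

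At stake is the timeliness of SAE reports and updates to the sponsor, and of the regulatory notifications that depend on them. Potential Hy's Law is one example. Section 10.3.2 lists it among important medical events, and Section 8.3.6 says of it: "For bimekizumab, the following event requires immediate reporting (within 24 hours, regardless of seriousness) to UCB".

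**Working it through.** The plan gives no figure to reproduce. The check compares the rules and follows a timeline.

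**Inputs**

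- Deadline: 24 h (Section 8.3.1).
- Paper trigger under Section 10.3.3: downtime of more than 24 h.
- Paper trigger under Section 10.7.6: any downtime.
- Assumption: the clock starts when the site becomes aware of the SAE (time 0), because Section 8.3.1 names no start point.

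Let the system fail at time s before the report has been entered (s is negative if it was already down at awareness), and let the outage last d hours. The electronic route reopens at s + d. Under Section 10.3.3 the paper route opens just after s + 24, and only if d exceeds 24.

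**Case 1, system already down at awareness (s < 0).** If d is at most 24, electronic entry is possible again at s + d, which is before 24 h. If d exceeds 24, paper opens just after s + 24, also before 24 h. Either way the duty can be met, with about −s hours or more to spare.

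**Case 2, system fails at or after awareness (0 ≤ s < 24).** The first route to open is the earlier of s + d and just after s + 24. The second is always past 24 h. The report is on time only if s + d is no more than 24, that is, if the system is back by the deadline. Otherwise the first route opens late by the smaller of s + d − 24 and just over s, so by less than 24 h.

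| System fails | Outage | First route under 10.3.3 | Against 24 h |
|---|---|---|---|
| 20 h before awareness | over 24 h | paper, just after −20 + 24 = 4 h | 20 h left |
| 1 h before awareness | over 24 h | paper, just after −1 + 24 = 23 h | 1 h left |
| at awareness | 6 h | electronic, 0 + 6 = 6 h | on time |
| at awareness | over 24 h | after 0 + 24 = 24 h | deadline passed |
| 10 h after awareness | 20 h | electronic, 10 + 20 = 30 h; paper never triggered | 6 h late |
| 10 h after awareness | 50 h | paper, just after 10 + 24 = 34 h | 10 h late |

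Under Section 10.7.6 the paper route opens as soon as the system is down, at s or at awareness if later. That is before 24 h in every row.

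**Cross-references.** The fallback sentence in Section 10.3.3 points to a next section for the paper tool, but Section 10.4, on contraception and pregnancy, comes next. The paper procedure appears only in Section 10.7.6. Section 8.3.1 also cites Appendix 4 (Section 10.4) for its 24-hour rule, although SAE procedures are in Appendix 3.

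**The case against.** The strongest reply is that nothing in Section 10.3.3 cancels the 24-hour duty. It says when paper becomes required and does not forbid paper earlier. A site reading the whole protocol is still bound by Section 8.3.1 and will find a workable rule in Section 10.7.6. Since every participant is dosed with a device presentation, that appendix can be read as covering SAEs in all four arms. Much of this stands: the duty survives, and a careful site can comply. What remains is that the site must depart from the trigger in the section it was sent to in order to meet the deadline, while the pointer to the paper procedure leads elsewhere.

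A reader might infer that any outage makes reports late, or that every SAE arising at the start of an outage is missed. The timeline does not support this: a 6-hour outage starting at awareness still allows an electronic report on time, and an outage already running at awareness leaves some room.

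A reader might also infer that late reports would delay a dosing hold under Section 7.1.1. The documents do not support that either. They describe no staged or cohort dosing, the hold can rest on the opinion of the investigator and/or the sponsor's study physician, and in this single-center study the investigator knows of the SAE without the electronic system.

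One limit applies: the separate SAE reporting page listed in the contents was not available for this review. It may give another route, but the sections quoted would still disagree.

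**Conclusion.** The conflict is real, and its consequence is conditional. Section 10.3.3 is inconsistent with Section 8.3.1 and with Section 10.7.6. A site following its trigger misses the 24-hour limit if three things coincide: the system fails at or after awareness, the report is not yet entered, and the system is still down at 24 hours. A failure shortly before awareness leaves little room. In a breach, the first prescribed route opens less than 24 hours after the deadline, and transmission time comes on top.

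This rests on counting from awareness. How often it would occur cannot be estimated, because the documents give neither outage frequency nor SAE counts. The issue concerns timely safety reporting to the sponsor and regulators. Sample size, analysis sets and the bioequivalence conclusion are unaffected. It is a correction that should be made, and not a flaw in the design.

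**What to change.** Reconcile Sections 8.3.1, 10.3.3 and 10.7.6.

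- Replace the fallback sentence in Section 10.3.3 with the Section 10.7.6 rule. In substance: when the electronic system is down, the site sends the SAE on the paper tool so that the sponsor has it within 24 hours, and enters it electronically once the system is back.
- In that sentence, replace the pointer to the next section with a reference to the paper reporting procedure in Section 10.7.6. Copying the Section 10.7.6 sentence unchanged would carry over a pointer that is wrong in its new place.
- In the same edit, correct the Appendix 4 citation in Section 8.3.1, state when the 24 hours start, and check that the SAE reporting page agrees.

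The cost is one sentence and a few references in the next amendment. The paper form and procedure already exist, and data collection and analysis do not change.
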